#### **Abstract**

Sexual and/or gender minority (SGM) people have disproportionately high rates of tobacco use – the number one cause of preventable death. Reasons for this include using tobacco to cope with social minority stressors, pro-tobacco use norms in SGM social spaces and networks, and targeted tobacco industry marketing. Empowerment Theory explains how positive behavior change, like quitting smoking, can be promoted through skills development with greater participation in the public affairs of one's community. An empowerment approach may enhance tobacco cessation treatment for SGM people and other stigmatized groups because it links individual well-being with the larger social and political context. This pilot study will assess the acceptability, feasibility, and preliminary impact of empowerment-enhanced tobacco smoking cessation assistance for SGM adults. We will enroll N=20 SGM adults in Oklahoma who smoke and are willing to quit. Participants will receive standard tobacco cessation assistance through the Stephenson Cancer Center Tobacco Treatment Research Program (TTRP). Concurrently, they will also engage in 'empowerment activities', meaning SGM organizing and community-building activities, like conducting follow up phone calls to participants of a gender marker and name change clinic. This will be facilitated by an Oklahoman SGM-serving community partner. Participants will complete 12 surveys during the intervention period and 12 weeks post-quit-date, a 60-minute, in-depth exit interview, and biochemically-verified smoking status before the intervention and 12 weeks post-quit-date. This pilot study will establish collaborative relationships between the PI's team and local SGM-serving organizations, and will produce preliminary findings to support future R01-level funding to conduct a fully powered randomized control trial of a multi-level empowerment-enhanced SGM tobacco cessation intervention.

#### **A. Specific Aims**

State the hypothesis and specific aims. List the long-term objectives and what the proposed research will accomplish.

**Aim 1: Assess the feasibility and acceptability of empowerment-enhanced tobacco cessation assistance for sexual and/or gender minority (SGM) adults.** We will use baseline and exit surveys and in-depth interviews to assess retention, empowerment activity participation (e.g., number, duration, intensity, roles), and participants' perceptions of the intervention.

**Aim 2: Compare individual empowerment and cessation predictors pre- and postintervention.** *Hypothesis:* Post intervention, participants will have (i) increased adaptive coping strategies, social support, and smoking abstinence self-efficacy; and (ii) decreased internalized SGM stigma.

**Aim 3: Assess tobacco cessation outcomes post-intervention.** *Hypothesis:* The proportion of participants with biochemically-verified smoking abstinence at 12 weeks post-quit-date will be equal to or greater than the general Stephenson Cancer Center Tobacco Treatment Research Program (TTRP) intervention (i.e., 18% biochemically-verified abstinence at 12 weeks); medication and counseling adherence will be moderate/optimal for >50% of treatment weeks.

We will produce preliminary data on a novel SGM tobacco cessation approach and establish collaborative relationships with SGM-serving organizations. Our findings will support a future NIH R01 to conduct a fully-powered randomized control trial of a multi-level empowerment-enhanced SGM tobacco cessation intervention. A longer-term research program will refine tobacco treatment strategies tailored to SGM individuals.

## B. Background and Significance

Tobacco use – the number one cause of preventable death – disproportionately impacts sexual and/or gender minority (SGM) groups. In the U.S., 30% of sexual minority people use tobacco versus 20% non-sexual minority, and gender minority people are 2–3 times more likely than cisgender people to use tobacco. Tobacco interventions that are tailored to priority groups, like SGM, aim to address unique drivers of use and barriers to cessation. Our work and others' shows that SGM tobacco use is linked to how SGM people interact with and negotiate everyday environments as a social minority person. Drivers of SGM tobacco use include social minority stressors, pro-tobacco norms in SGM social networks and spaces, and targeted tobacco industry marketing. This is particularly true in states with high levels of structural SGM stigma, like Oklahoma (OK). SGM Oklahomans experience disproportionate mental health and material hardship and our preliminary data show that sexual minority adult Oklahomans are at greater risk for past 30-day tobacco use (51.6%) than non-SGM (40.4%). Yet, tobacco cessation assistance tailored for SGM Oklahomans is unavailable.

The past decade has seen increasing interest in tailoring tobacco control interventions to SGM people. While a minority of interventions engage with SGM social networks and spaces, most focus on individual-level factors (e.g., readiness to quit) and may not be equipped to address the unique person-environment drivers of SGM tobacco use. An Empowerment Theory (ET) approach to tobacco cessation may enhance efficacy for SGM Oklahomans because it links individual well-being with the larger social and political context. ET asserts that positive behavior change can be promoted through skills development with greater participation in the public affairs of one's community. Individual

empowerment outcomes may include perceptions of personal control and a proactive approach to life. Efforts to exert control are central to ET approaches; empowering processes often involve participation with others to achieve goals, efforts to gain access to resources, and opportunities to more critically understand one's sociopolitical environment.

ET approaches have not been used in SGM-tailored tobacco interventions, but have been shown to be efficacious, feasible, and acceptable for use in SGM HIV/STI prevention and youth-tailored tobacco interventions. For SGM people, SGM-related social change mobilization and community-building participation are linked to empowering outcomes, including more adaptive coping with minority stress, experiencing more meaning in life, greater community connection, and overall positive psychological functioning. Minority Stressguided research on SGM people shows that as levels of coping and social support increase, so does engagement in health-promoting lifestyles. For SGM smokers, adaptive coping strategies, social support, smoking abstinence selfefficacy, and internalized SGM stigma may influence tobacco use and cessation behaviors, suggesting that empowerment activities may indirectly support tobacco cessation among SGM. We will pilot a novel tobacco cessation intervention that uses an empowerment approach focused on SGM community building to enhance smoking cessation outcomes for SGM Oklahomans.

**This project is innovative because it is:**

- A novel application of a theoretical framework, Empowerment Theory, from parallel health behavior change fields to advance tobacco cessation assistance for a social group with persistent tobacco-related disparities.
- The first SGM-tailored tobacco cessation intervention to integrate SGM empowerment activities with tobacco cessation assistance best practices to address person-environment drivers of SGM tobacco use.
- The first SCC partnership with an SGM-serving organization to reduce SGM Oklahoman tobacco use.

**C. Preliminary Studies/Progress Report**

1. Provide an account of previous studies and/or information that establishes the experience and competence of the investigator to pursue the protocol.

**Team Expertise and Preliminary Data.** Our team brings the requisite expertise in SGM tobacco disparities, tobacco cessation assistance for priority groups, community-engaged interventions, and SGM empowerment. PI [name], Co-I [name], and Drs. [name] and [name]'s work shows the person-environment relationship drivers of SGM tobacco use, including using tobacco to cope with social minority stressors like fear of rejection and harassment. Co-I [name] is PI of the SCC Tobacco Treatment and Research Program (TTRP), which will assist with study recruitment and enrollment and provide standard tobacco cessation treatment. Co-I [name] has expertise in biostatistical analysis of TTRP data. Drs. [name], [name], [name] and Co-I [name] have expertise

in tobacco and other health interventions for priority groups, including SGM, Latinx, and socioeconomically disadvantaged. PI [name]'s evaluation of a bar-based tobacco intervention for high-risk young adults found that immersive experiences that encourage a sense of collective purpose may enhance endorsement of anti-tobacco messaging. [name] has over 15 years of experience developing social change and community-building programming for priority communities, including SGM groups in Oklahoma.

#### **D. Research Design and Methods (What, When, How, Where)**

**Study overview.** This study will assess the feasibility and acceptability of empowerment-enhanced tobacco cessation assistance for SGM adults. We will use a single-arm pilot design given funding, time, and sampling pool limits. Participants (N=20) will receive standard TTRP tobacco cessation assistance and concurrently participate in SGM empowerment activities. We will assess outcomes quantitatively and qualitatively. Primary outcome variables will be retention, perceptions of the intervention, adaptive coping strategies, biochemically-verified smoking abstinence at 12 weeks post-quit-date, and treatment adherence.

**Recruitment.** We will enroll participants over a 4-month period and recruit through the TTRP, which serves an average of 30 SGM individuals per year without SGM-targeted recruitment. We will supplement this by recruiting via local SGM-serving organizations, SGM targeted social media ads (e.g., Facebook), and snowball recruitment.

**Eligibility criteria:** Self-identify as SGM, 18+ years of age, report past 30-day combustible tobacco use (i.e., current smokers), willing to quit in the next two weeks, no contraindications for nicotine replacement therapy (NRT), reside in OK (verified with valid ID), willing to refrain from smoking any substance (e.g., cannabis) within 48 hours of expired carbon monoxide collection as this may impact biochemically-verified smoking abstinence.

**Demographic sampling.** Our racial and ethnic identity sampling targets roughly reflect the general Oklahoma population. The largest racial and ethnic groups in Oklahoma are Non-Hispanic White (65%), Hispanic (11.1%), American Indian (9.4%) Black/African American (7.8%), and two or more races (6.3%). For gender targets, we aim to recruit for an approximately even number of cisgender female, cisgender male, and 'other gender' identifying participants (e.g., transgender, gender non-conforming, gender queer, refuse to answer). Approximately 3% of the general TTRP participant pool identify within this 'other gender' identity group. We will aim to over-recruit for 'other gender' identifying participants given the SGM focus of this pilot study. For sexual identity, our recruitment aims will reflect the non-heterosexual identity groups in the TTRP participant pool; the largest of these is gay/lesbian (4.9%), followed by 'unsure or refused to answer' (2.5%) and bisexual (2%).

**Intervention.** Participants will receive standard TTRP tobacco cessation assistance either remotely or in-person: 6 weekly counseling sessions and 12 weeks of

combination NRT (nicotine patches + nicotine gum or lozenges). During the 6 weeks of counseling, participants will also engage in 4 ‘empowerment activities’ (i.e., SGM social change mobilization and community building activities) lasting approximately 1.5 hours each, with the option to do more if desired. Activities will be tailored to each participant’s comfort level and scheduling restraints.

Below is a list of empowerment activities that may be offered to participants:

- Compile publicly available, online information about school board meetings (locations, times, board contact information) into a spreadsheet. This spreadsheet will be made available to the public online to make it easier for people to be involved in their local schools.
- Conduct online research regarding HIV resources and services (for example, testing sites) in Oklahoma and compile into a word document. This will be made available to the public online to make it easier for people to access HIV resources in Oklahoma.
- Conduct phone calls using a script to gender marker and name change clinic participants to assess their needs and report those needs back to the clinic.
- Conduct online research on the process to change gender markers and names in Oklahoma to be compiled into a resource document that will be made available to the public online.
- Support preparation for public webinars to raise community awareness about local LGBTQ2S+ resources by conducting phone calls to community members who are part of Freedom Oklahoma’s network to assess what they would like to learn about in the webinars.
- Support in-person community engagement events, like the community gala skate night, by helping with event registration, event set-up, and event take down.

Participants will complete the following assessments: (i) 12 surveys (baseline, exit, quit-day, 1-4 and 12 weeks post-quit-date, and immediately following ‘empowerment activity’ participation for up to 4 sessions; (ii) biochemically-verified smoking status at baseline and 12 weeks post-quit-date via expired carbon monoxide monitors; and (iii) a 60-minute in-depth interview over Zoom video chat within weeks 6-8 post-quit-date. Participants will be incentivized a total of \$300 for the baseline survey (\$25), 6 subsequent short surveys (\$70), 4 empowerment activity feedback surveys (\$100), 2 expired carbon monoxide tests (\$20), , exit survey (\$25), and 60-minute interview (\$60). Participants are also eligible to receive up to two additional incentive bonuses for assisting in snowball recruitment of eligible participants who enroll in this study (\$25 per referral, maximum of \$50). Participants will be eligible for up to a \$350 incentivized total. Freedom Oklahoma staff will participate in interviews and reflect on the intervention and Freedom OK’s role in it. Freedom Oklahoma will adopt a tobacco-free policy and provide feedback on the cultural competence of TTRP materials.

**Partnerships.** TTRP will provide the standard tobacco cessation assistance. Freedom Oklahoma will design the empowerment activities. Freedom Oklahoma is a community-based organization in Oklahoma City that has worked to secure lived equality and legal protection for SGM Oklahomans for over 15 years. PI [name] and Freedom OK have held more than 4 project planning meetings over the past year.

**Measurement of Feasibility and Acceptability (Aim 1).** We will use exit surveys and empowerment activity feedback surveys administered via REDCap to assess retention and self-reported empowerment activity participation (i.e., total hours, types of events/activities, roles played). We will cross-reference with research project records of empowerment activity participation. We will also qualitatively assess perceptions of the intervention by interviewing participants over Zoom video chat at 12 weeks post-quit-date. PI [name], a qualitative methods expert, will train a team to conduct semi-structured, in-depth interviews lasting approximately 60 minutes. We will elicit rich content regarding experiences of empowerment activity participation and tobacco cessation as an SGM person in Oklahoma. Interview guide domains will include: (i) best intervention aspects (e.g. highlights, peak experiences); (ii) biggest challenges or negative experiences; (iii) empowerment activity experiences; (iv) interactions of empowerment activity participation with tobacco cessation experiences; (v) outcomes and personal growth (vi) suggestions for intervention improvements. Interviews will be audio-recorded and professionally transcribed verbatim.

**Qualitative Analysis:** We will use Dedoose qualitative data analysis software to conduct an inductive-deductive thematic transcript analysis with a priori themes derived from ET and SGM tobacco cessation literature. We will use an iterative codebook development process involving weekly team discussions, independent coding, and member checking of findings to enhance rigor and trustworthiness. We will also interview Freedom Oklahoma staff about their perceptions of the intervention and their organization's role in it.

**Measurement of Individual Empowerment and Cessation Predictors (Aim 2).** We will compare individual empowerment and cessation predictors pre- and postintervention with baseline and exit surveys. We will assess predictors of smoking cessation and individual empowerment outcome measures adapted from a youth empowerment tobacco control model and SGM social change mobilization participation research. These will include: (i) adaptive coping strategies (Cognitive Emotion Regulation Questionnaire), (ii) (v) social support (Relational Health Indices), (iii) abstinence self-efficacy (Confidence Inventory), and (iv) internalized SGM stigma (Internalized Transphobia and Pride and Internalized Homophobia items).

**Measurement of Tobacco Cessation Outcomes (Aim 3).** We will use benchmarks to assess participants' tobacco cessation outcomes. Tobacco abstinence will be measured via self-report and biochemically-verified via expired carbon monoxide at baseline and 12 weeks post-quit-date. Treatment adherence will be assessed with

the 4-item Medication Adherence Questionnaire (MAQ) and counseling session attendance tracking.

**Sample Size/Analysis Plan.** Primary outcome variables will be: retention, perceptions of the intervention, adaptive coping strategies, biochemical verification of tobacco abstinence at 12 weeks post-quit-date, and treatment adherence. We will evaluate retention by calculating the proportion of participants who complete the final study visit at 12-weeks post-quit, with the goal of retaining >80% of participants. We will qualitatively evaluate perceptions of the intervention (as described above). We will use a two-sided paired samples t-test to examine the mean differences in adaptive coping strategies pre- and postintervention ( $\alpha=0.05$ ). Assuming 20% attrition and a standard deviation of differences of 4.0^85,  $n=20$  participants will provide 80% power to detect a mean difference of 2.6 in adaptive coping strategies. Tobacco cessation outcomes will be considered successful if the proportion of participants with biochemically-verified smoking abstinence (expired carbon monoxide) at 12 weeks post-quit date is equal to or greater than the general TTRP sample (i.e., 18% at 12 weeks). Treatment adherence will be considered successful with all participants having >50% of treatment weeks with an MAQ score indicating moderate/high adherence and counseling session attendance.

Expected outcomes: Empowerment-enhanced tobacco cessation assistance will be acceptable and feasible (Aim 1), will increase within-subject empowerment and improve cessation predictors (Aim 2), and will meet benchmarks for tobacco cessation outcomes (Aim 3).

Identifiers might be removed and the de-identified information may be used for future research without additional informed consent from the subject.

**Potential problems and alternative strategies.** COVID-19: All intervention activities can be conducted remotely, including cessation counseling, empowerment activities (e.g., remote phone banking), and mailing iCOquit devices (expired carbon monoxide) to participants. Retention: We budgeted for 25 participants to allow for a 20% drop out rate. Some participants may not find certain empowerment activities acceptable and will be encouraged to continue TTRP tobacco cessation assistance. Recruitment: We have budgeted for contingency recruitment efforts, including contracting a specialized recruitment service (e.g., TrialFacts) and distributing press releases to regional media outlets.

**Timeline.** Month 1 Study preparation; Months 2-6 Recruitment and enrollment; Month 10 All 12-week follow-up visits will have concluded; Month 10-12 Data analysis and manuscript preparation.

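### With 20 enrolled and 20% lost, the two-sided paired t-test on coping has about 68% power for a 2.6-point change, not 80%; the protocol does not settle whether 20 or 25 will be enrolled

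*Protocol*

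**What the plan says.** Adaptive coping is one of five primary outcomes. For it, protocol section D (Sample Size/Analysis Plan) states: "We will use a two-sided paired samples t-test to examine the mean differences in adaptive coping strategies", at alpha 0.05. Assuming 20% attrition and a standard deviation of paired differences of 4.0, it says that 20 "participants will provide 80% power to detect a mean difference of 2.6 in adaptive coping strategies". Section M repeats this.

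The sample size appears in several places:

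- Abstract: "We will enroll N=20 SGM adults in Oklahoma who smoke and are willing to quit".
- Section D, Study overview: "Participants (N=20) will receive standard TTRP tobacco cessation assistance".
- Section J: 20 participants are to be enrolled over four months.
- Section D, Potential problems and alternative strategies: "We budgeted for 25 participants to allow for a 20% drop out rate".

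On the source of the pairs, section D (Aim 2 measurement) says: "We will compare individual empowerment and cessation predictors pre- and postintervention with baseline and exit surveys". The assessment schedule lists "12 surveys (baseline, exit, quit-day, 1-4 and 12 weeks post-quit-date", so the exit survey is separate from the 12-week survey and has no date.

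The SAP keeps the two-sided test, the 4.0, the 80% and the 2.6, but gives no sample size and no attrition rate.

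**The concern.** The power sentence names 20 participants and 20% attrition together. The Abstract and section J say that 20 is the number enrolled. Read together, the paired test has 16 pairs, and the stated 80% should hold at 16. It does not.

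Coping is the only primary outcome with a planned hypothesis test and the only one with a power statement. If the figure is wrong, the chance of missing a true 2.6-point change is understated. A reader also cannot tell how many people the study will enrol or how many pairs the test expects.

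**Working it through.** **Inputs, all from protocol sections D and M unless noted:** two-sided paired t-test, alpha 0.05; SD of differences 4.0; mean difference 2.6; attrition 20%; 20 enrolled (Abstract, section J); 25 budgeted (section D, Potential problems).

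**Pairs.** 20 × 0.80 = 16. On the budget figure, 25 × 0.80 = 20.

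**Formula.** With n pairs, the test statistic follows a noncentral t distribution with n − 1 degrees of freedom and noncentrality (2.6/4.0) × √n = 0.65 × √n. Power is the probability that it falls beyond ±t(0.975, n − 1).

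**The plan's figure with its own inputs.** For n = 16, the noncentrality is 0.65 × 4 = 2.60 and the critical value is 2.131 on 15 degrees of freedom. Power is 68.1%, so the stated 80% is not reproduced. A simulation of 400,000 trials gave 68.2%.

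**Other numbers of pairs, two-sided:**

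| Pairs | Power for 2.6 | Difference detectable with 80% power |
|---|---|---|
| 16 | 68.1% | 3.00 |
| 17 | 71.1% | 2.90 |
| 18 | 73.9% | 2.80 |
| 19 | 76.4% | 2.72 |
| 20 | 78.7% | 2.64 |
| 21 | 80.9% | 2.57 |

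Seventeen is the fewest completers that meets the retention aim ("with the goal of retaining >80% of participants") with 20 enrolled, since 16/20 is exactly 80%. Reaching a full 80% needs 21 pairs, or 21/0.80 = 26.25, so 27 enrolled.

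**Could something else explain 80% at 16 pairs?**

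- *Rounding.* Taking 2.6 as high as 2.649 and 4.0 as low as 3.95 gives 70.8%.
- *Normal approximation.* The detectable difference is (1.960 + 0.842) × 4.0/√16 = 2.80, still above 2.6.
- *A smaller SD.* Power reaches 80% only if the SD is about 3.47.
- *A one-sided test at 0.05.* Power is 79.8% and the detectable difference 2.61. This fits numerically but contradicts the stated two-sided test.

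Two routes therefore lead to about 80%: 20 analysed pairs with a two-sided test, or 16 pairs with a one-sided test. Each drops something the protocol states, and the documents do not say which was used.

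**The case against.** The best defence is that 20 means completers. The remark about 25 participants is an explicit retention allowance at the same 20% rate, and 25 × 0.80 is exactly 20. At 20 pairs the detectable difference is 2.64, which rounds to 2.6. The power sentence can be read as 20 people remaining after attrition. On that reading the power figure is sound and the fault is an unreconciled 20 versus 25.

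This is a plausible account of where 2.6 came from, but it moves the error without removing it: the Abstract and section J, which say that 20 will be enrolled, become wrong. The figure of 25 appears only as a budget remark and is nowhere stated as the enrolment target.

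It is also fair that nothing in the documents suggests a one-sided calculation beyond the numerical match. That supports asking the question and no more.

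The practical weight is limited. The SD of 4.0 rests on a cited source that is not available here. For an assumed range of 3.5 to 4.5, power at 16 pairs runs from 79% to 58%, a wider spread than the gap of about 11 points between 16 and 20 pairs. No success rule depends on this test, and section O disclaims firm conclusions from so small a sample. These points limit the consequence; they do not make the stated figure follow from the stated inputs.

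**Conclusion.** The concern holds. With 20 enrolled, 20% of pairs lost, an SD of 4.0 and a two-sided 0.05 test, power for 2.6 is 68.1%. A true change of that size would be missed about 32% of the time rather than 20%, and the difference detectable with 80% power is 3.0.

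The size of the shortfall depends on two things. The first is that baseline/exit pairs are lost at the stated 20%; because the exit survey is undated, pair loss could differ from loss at the 12-week visit. With 20 enrolled, power ranges from 68.1% at 20% loss to 78.7% at none, so the shortfall is negligible only if almost no pairs are lost. The second is that 20 is the enrolment figure. If 25 are enrolled, the power statement is about right and the enrolment statements need correcting.

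The plan should be corrected either way, although the consequence for a single-arm feasibility pilot is modest.

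**What to change.** Confirm that the calculation was two-sided. Then state enrolled and analysed numbers separately, and use the same pair in the Abstract, section D (Study overview and Sample Size/Analysis Plan), section J, section M and the SAP.

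- **If 20 is the target:** 20 enrolled, 16 analysed after 20% attrition; 80% power for a mean difference of 3.0, and about 68% for 2.6, two-sided. Only wording changes.
- **If 25 is the target:** 25 enrolled, 20 analysed after 20% attrition; about 80% power for 2.6 (exactly 78.7%). The enrolment statements change from 20 to 25.

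The second option means recruiting five more people, who according to section D are already budgeted. At 30 SGM clients a year, the TTRP supplies about 30 × 4/12 = 10 in the four-month window of section J, even if all of them join. At least 15 rather than 10 must then come from other channels. The Timeline's months 2 to 6 may allow a fifth month (30 × 5/12 = 12.5, or about 12 from the TTRP and 13 from elsewhere), and section D also budgets for contingency recruitment.

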**J. Recruitment and Enrollment**

1. Describe the plans for recruitment.

a. Methods to identify and recruit potential participants

We will enroll participants (N=20) over a 4-month period and recruit through the Tobacco Treatment Research Program (TTRP), which serves an average of 30 sexual and/or gender minority (SGM) individuals per year without SGM-targeted recruitment efforts. We will supplement this pool of SGM participants by recruiting for SGM participants through local SGM-serving organizations, SGM targeted social media ads (e.g., Facebook), and snowball recruitment.

- Tobacco Treatment Research Program (TTRP) enrollments. The Stephenson Cancer Center's TTRP follows an Institutional Review Board (IRB)-approved research protocol where participants are referred by a health care provider through the University of Oklahoma Health Sciences Center (OUHSC) electronic medical record. Community participants may contact the clinic via the web, email, phone, fax, walk-in and tablet connection (in certain circumstances). The TTRP responds to referrals by providing information about treatment options, screening participants, and scheduling them for standard TTRP treatment or for an ongoing trial (if eligible and interested).
- Local sexual and/or gender minority (SGM)-serving organizations. Freedom Oklahoma, a SGM-serving organization in Oklahoma City and the community partner on this proposal (See Letter of Support) will distribute recruitment materials to their extensive professional networks and channels of communication and will connect the research team to additional SGM-serving community organizations as needed to diversify the sample. Physical materials with study information will be printed as needed for distribution by SGM serving community organizations in Oklahoma and posted in public spaces (e.g., palm cards, flyers).
- Targeted social media campaign. Participants will be recruited through paid advertisements on Facebook and Instagram that target SGM people who use tobacco and live in Oklahoma using a well-established campaign program managed by the University of Oklahoma Marketing team. Additional recruitment advertisements will be posted on Craigslist or other local advertising services and online forums as needed.
- Snowball recruitment. Participants will be invited and incentivized (\$25 per referral of an eligible individual who enrolls in the study for a maximum of two

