Detailed protocols are in place to assess participant safety and respond effectively throughout participant engagement in this empowerment-enhanced tobacco cessation intervention pilot study, and to minimize risk of loss of participant confidentiality and data storage procedures.

**General Procedures:** Each participant will be assigned an identification number that will be utilized in place of names in all electronic and print data

files. The file containing the links between participant names and identifiers will be kept in a separate password-protected file, which will be destroyed 12 months after the completion of the study. Any print information will be stored in a locked filing cabinet in the Principal Investigator's locked office. Electronic data (with names omitted) will be maintained on the investigator's computers, and all computers and electronic files will be password protected. Biochemical verification of smoking status will be collected in a private room in the TTRP. All project staff will complete extensive training focused on each of the following topics: 1) project rationale and objectives, 2) the informed consent process, 3) general data collection procedures (e.g., computer data collection, privacy), and 4) use of the carbon monoxide monitor.

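### Does the 18% abstinence rule need a stated denominator and a rule for a missing week-12 carbon monoxide reading?

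*Protocol*

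**What the plan says.** The cessation rule stands in the Sample Size/Analysis Plan paragraph of protocol section D, is repeated in section M, and appears in near-identical form in the SAP. The proportion of participants with abstinence verified by expired carbon monoxide (CO) at 12 weeks post-quit-date succeeds if it "is equal to or greater than the general TTRP sample (i.e., 18% at 12 weeks"). Aim 3 in section A sets the same benchmark.

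The same paragraph defines retention as the "proportion of participants who complete the final study visit at 12-weeks post-quit", with a goal above 80%. Its power sentence, in the protocol versions, assumes 20% attrition and says that 20 "participants will provide 80% power to detect a mean difference of 2.6 in adaptive coping strategies".

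On numbers, section J says "We will enroll participants (N=20) over a 4-month period", and the Abstract and the study overview in section D also give 20. Under potential problems, section D adds: "We budgeted for 25 participants to allow for a 20% drop out rate".

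On the readings, the eligibility criteria in section D ask participants to refrain from smoking any substance "within 48 hours of expired carbon monoxide collection as this may impact biochemically-verified smoking abstinence". The COVID-19 contingency allows "mailing iCOquit devices (expired carbon monoxide) to participants", while section K says "Biochemical verification of smoking status will be collected in a private room in the TTRP". Section H.3 ends participation for people who stop taking part and do not respond to repeated contact, without saying how their outcome is coded. Neither document has a general missing-data rule.

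**The concern.** Abstinence is a listed primary outcome with a pass/fail threshold, in a sample so small that one person moves the rate by five percentage points (1/20). If the denominator were open, one and the same number of quitters could be called success or failure, and the choice could be made after the data were seen.

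Three features make it look open. No sentence deals with a missing reading. The word *participants* seems to shift in meaning: in the retention sentence it must cover everyone enrolled, whereas the power sentence roughly reproduces only if 20 is the number left after drop-out. And readings might be lost for reasons other than drop-out, given the condition about other smoked substances and the two collection settings. It is also not stated how the programme's own 18% treated people without a reading.

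**Working it through.** **Inputs.** Threshold 18%; 20 enrolled (Abstract, sections D and J); 25 budgeted (section D); attrition 20%; SD of differences 4.0, mean difference 2.6, two-sided alpha 0.05 (sections D and M). The 10% attrition used below is an assumption.

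**1. The plan's own power figure.** For a paired t-test with n pairs, the noncentrality is (2.6/4.0) × √n on n − 1 degrees of freedom.

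| Pairs | Noncentrality | Power at 2.6 | Difference detectable with 80% power |
|---|---|---|---|
| 20 | 2.91 | 78.7% | 2.64 |
| 16 (= 20 × 0.80) | 2.60 | 68.1% | 3.00 |

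The stated 80% is roughly reproduced with 20 analysed pairs, not with 16. That is the only basis for a second meaning of *participants*.

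**2. Where the verdict could turn.** The least number of quitters that passes is 0.18 × denominator, rounded up.

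| Enrolled | Readings | Needed over all enrolled | Needed over those read | Count that differs |
|---|---|---|---|---|
| 20 | 16 | 3.60 → 4 | 2.88 → 3 | 3: 15% v 18.75% |
| 20 | 17 to 20 | 4 | 3.06 to 3.60 → 4 | none |
| 25 | 20 | 4.50 → 5 | 3.60 → 4 | 4: 16% v 20% |
| 25 | 21 or 22 | 5 | 3.78 or 3.96 → 4 | 4: 16% v 19.0% or 18.2% |
| 25 | 23 to 25 | 5 | 4.14 to 4.50 → 5 | none |

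On the stated enrollment of 20, the denominators can disagree only with 16 or fewer readings. Meeting the retention goal means at least 17 of 20 final visits, and if each yields a reading the verdict is the same either way.

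**3. How often they would disagree.** Take 18% as the rate among all enrolled, with everyone lacking a reading still smoking (assumption). The rate among those read is then 0.18/0.80 = 0.225.

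- Exactly 16 of 20 read: P(3 of 16) = 23%. Exactly 20 of 25 read: P(4 of 20) = 21%. If 18% is instead the rate among those read, these become 25% and 21%.
- Number of readings binomial with 20% missing on average: 15% (20 enrolled), 20% (25 enrolled).
- With 10% missing on average (rate among those read 0.18/0.90 = 0.20): 3% and 10%.

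**4. What the wording yields.** Numerator: participants whose abstinence was biochemically verified. Someone with no reading has no verification and cannot be in it. Denominator: participants, not completers or those assessed. With 20 enrolled, 16 readings and three quitters, this gives 3/20 = 15%, a fail. An added sentence defining the denominator as all enrolled and a missing reading as not verified would also give 3/20. The two agree for every count and every level of attrition.

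**The case for a change.** The strongest case for a change is that a pass/fail rule on a primary outcome should leave no choice for later, that a sentence costs almost nothing, and that the disagreement arises at the plan's own attrition figure. Retention counts visits and not usable readings, so 18 of 20 visits with two unusable readings would still leave 16. With 25 enrolled, the disagreement persists at 21 and 22 readings, which is above 80% retention. The pilot also feeds a grant application.

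The arithmetic stands, and so does the plain fact that no missing-reading sentence exists. The rest is weaker.

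- The second meaning of *participants* is back-calculated from the power statement for the coping outcome. A loose sample-size sentence does not redefine the denominator of another outcome, and the SAP paragraph contains neither the 20 nor the attrition figure.
- Twenty-five is a budget allowance; every statement of enrollment says 20.
- The condition about other smoked substances is there to prevent interference. Such smoking would be expected to give a raised reading that fails to verify abstinence, not a missing one. The mailed-device and clinic-room statements concern where a reading is taken. Neither shows readings being lost beyond drop-out.
- How the 18% counted people without a reading is unknown from these documents. That limits how the comparison is interpreted, but it does not leave this trial's own proportion undefined.

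One related matter is separate: 20 enrolled less 20% leaves 16 pairs and about 68% power for a difference of 2.6. That belongs to the coping power statement and does not bear on how abstinence is counted.

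**Conclusion.** No change to the plan follows. This is an unwritten detail that the wording already settles: verified abstainers over all participants, with a person lacking a reading counted as not verified. A sentence saying so would reproduce the result that the plan already gives.

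The verdict could differ only if an analyst left that wording for an assessed-only denominator. On the stated enrollment of 20, this needs 16 or fewer readings and then a quitter count on the boundary, such as three of 16. The chance is about 15% with attrition varying around 20%, and 3% with attrition averaging 10%. Both figures assume a true rate equal to the benchmark and no quitters among those without a reading. The figures of 21% to 25% require exactly a fifth of readings to be missing.

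The consequence is also bounded. Section O says that the small sample will not support conclusions, and neither document ties a go/no-go decision to the 18% rule. The exact 95% intervals for 3/16 (4.0% to 45.6%) and 4/20 (5.7% to 43.7%) overlap almost entirely. A report giving the number of quitters, the number read and the number enrolled lets any reader form either rate.
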